8.5 Additional Efficacy Analyses

8.5.1 Endpoints related to DYS, NMPP, Dyspareunia and Overall endometriosis-associated pain

The proportion of responders at Months 1 – 12 based on change from baseline in average pain scores (DYS, NMPP, or dyspareunia) and analgesic use criteria (as defined in [Table 1](#)) will be analyzed using a logistic regression model with the responder/non-responder categorization as the dependent variable, treatment as the main effect, and baseline pain score (DYS, NMPP or dyspareunia) as a covariate. The proportion of responders, difference in proportions between elagolix plus E2/NETA group and placebo group, and odds ratio with corresponding 95% CI and P values will be presented. The pain threshold for defining responders will be determined using the same ROC analysis

described for the co-primary endpoints. Details of the ROC analysis are presented in [Appendix A](#) and the pain threshold values (X) are presented in [Appendix C](#). The same analyses will be repeated for the proportion of responders at Months 1 – 12 based only on change from baseline in average pain scores (DYS, NMPP, or dyspareunia). The responder analysis will be using the LOCF approach.

In addition, the proportion of responders at Months 1 – 12 based on change from baseline in average pain scores (DYS, NMPP, or dyspareunia) and analgesic use criteria and proportion of responders based on change from baseline in average pain scores (DYS, NMPP, or dyspareunia) only will also be summarized by treatment group using observed cases.

The change from baseline to each month in *DYS*, *NMPP*, *Dyspareunia*, and overall endometriosis-associated pain during the 12-month placebo-controlled Treatment Period will be evaluated using MMRM analysis. The MMRM analysis will include the fixed categorical effects of treatment, visit, and treatment-by-visit interaction, and the continuous fixed covariate of baseline pain score. A random subject effect term is included to account for the correlation among the repeated measurements in the changes from baseline. The selection and use of the covariance structure used in this analysis will follow the same process as described previously for the ranked secondary endpoints in [Section 8.4.1.1](#). The LS mean and standard error will be reported for each treatment group; the LS mean of treatment difference and associated 95% CI and P value will be reported comparing elagolix plus E2/NETA group against placebo group.

In addition, the change from baseline to each month in *DYS*, *NMPP*, *dyspareunia*, and overall endometriosis-associated pain during the 12-month placebo-controlled Treatment Period will be summarized by treatment group using observed cases. The change from baseline to each monthly visit in overall endometriosis-associated pain during the open-label Treatment Period will also be summarized by treatment group using observed cases.

In addition, the following plots will be provided using observed cases:

- Cumulative distribution function for reduction from baseline in DYS, NMPP, and dyspareunia to Months 1 – 12.

8.5.2 Rescue Analgesic Use for Endometriosis-Associated Pain

The monthly average rescue medication pill counts as collected in the e-diary will be summarized using observed cases only with descriptive statistics by treatment group for the categories of analgesic use – NSAIDs, opioids, any class of analgesic medications (NSAIDs or opioids), and both classes of analgesic medications (NSAIDs and opioids) during the 12-month placebo-controlled Treatment Period.

For the following categories of analgesic use – NSAIDs, opioids, any class of analgesic medications (NSAIDs or opioids), and both classes of analgesic medications (NSAIDs and opioids), the change from baseline to each month during the 12-month placebo-controlled Treatment Period will be evaluated using an MMRM analysis. The MMRM analysis will include the fixed categorical effects of treatment, visit, and treatment-by-visit interaction, and the continuous fixed covariate of baseline analgesic use. A random subject effect term is included to account for the correlation among the repeated measurements in the dependent variable. The selection and use of the covariance structure used in this analysis will follow the same process as described previously for the ranked secondary endpoints in Section 8.4.1.1. The LS mean and standard error will be reported for each treatment group; the LS mean of treatment difference and associated 95% CI and P value will be reported comparing elagolix plus E2/NETA group against placebo group. In addition, the change from baseline to each monthly visit during the 12-month placebo-controlled Treatment Period will be summarized by treatment group using observed cases.

Proportion of responders based solely on the change from baseline in analgesic use will be summarized by treatment group at each visit during the 12-month placebo-controlled Treatment Period using the observed cases. Definition of analgesic use responder will be based on Table 1. In addition, the proportion of responders will be analyzed using a chi-square test based on LOCF approach. The difference in proportions between elagolix plus

E2/NETA group and placebo group, and odds ratio with corresponding 95% CI and P values will be presented.

The proportion of responders for each category in [Table 1](#) during the 12-month placebo-controlled Treatment Period will be summarized using LOCF for elagolix plus E2/NETA group and placebo group. In addition, the proportion of responders for each category in [Table 1](#) during the 12-month placebo-controlled Treatment Period will be summarized by treatment group using observed cases.

For both NSAIDs and opioids, the monthly average rescue medication pill counts as collected in the e-diary will be summarized by medication name and treatment group using observed cases during the 12-month placebo-controlled Treatment Period. In addition, number of subjects who switch NSAID and opioid medication at baseline, Month 6, and any time from Baseline to Month 6 during the placebo-controlled Treatment Period will be summarized.

In addition, the standardized monthly average rescue medication pill counts as collected in the e-diary for both NSAIDs and opioids will be summarized by treatment group using observed cases during the 12-month placebo-controlled Treatment Period. The following rule will be used to standardize NSAIDs and opioid:

- NSAIDs: 1 pill Naproxen = 1 pill Ibuprofen = 1 pill Diclofenac = 4 pills Celecoxib = 1 pill of NSAID use;
- Opioids: 1 pill hydrocodone + acetaminophen = 1 pills codeine phosphate + acetaminophen = 1 pill of opioid use.

The monthly total rescue medication pill counts as collected in the e-diary will be summarized using observed cases only with descriptive statistics by treatment group for the NSAIDs and opioids use during the placebo-controlled Treatment Period.

For subjects with at least 1 pill use of NSAIDs at baseline, the number and percentage of subjects who are off NSAIDs use at each month will be summarized using observed cases. In addition, for subjects who didn't use NSAIDs at baseline, the number and percentage of

subjects who take at least 1 pill count of NSAIDs at each month will be summarized using observed cases. Same analyses will be repeated for opioids.

8.5.3 Patient Global Impression of Change (PGIC)

During the 12-month placebo-controlled Treatment Period and open-label Treatment period, PGIC will be summarized by treatment group using the observed cases. In addition, PGIC will be summarized for elagolix plus E2/NETA group and placebo group during the 12-month placebo-controlled Treatment Period using LOCF approach.

Categorical summary of the PGIC results during the Treatment Period will be presented as follows.

- The number and percentage of subjects in each PGIC response category (7-point scale) will be summarized. No statistical tests will be performed.
- The response categories of "Very Much Improved" and "Much Improved" will be combined and labeled as "Much Improved or Better." The remaining five categories of the PGIC scale will be combined and labeled "Otherwise." The number and percentage of subjects with response of a) "Much Improved or Better" and b) "Otherwise" will be summarized. Elagolix plus E2/NETA group will be compared with placebo using a chi-square test at each of Months 1 – 12. No statistical tests will be performed at Months 13 – 48.

8.5.4 Endometriosis Health Profile Questionnaire (EHP-30)

EHP-30 data will be summarized and analyzed using observed cases. Missing data will not be imputed.

EHP-30 data will be summarized for the five dimensions of the core questionnaires (Pain, Control and Powerlessness, Emotional well-being, Social Support, Self-Image) and the dimension of sexual intercourse of the modular questionnaire during the Treatment Period.

During the 12-month placebo-controlled Treatment Period, the change from baseline to each scheduled assessment for each dimension of the EHP-30 will be evaluated using an ANCOVA model with treatment as the main effect and baseline as a covariate. The LS mean and standard error will be reported for each treatment group; the LS mean of treatment difference and associated 95% CI and P value will be reported comparing elagolix plus E2/NETA group with placebo.

In addition, the change from baseline to each scheduled assessment for each dimension will be summarized with descriptive statistics during the Treatment Period. No comparisons or statistical tests will be performed.

8.5.5 EuroQoL-5D 5 Level (EQ-5D-5L)

EQ-5D-5L data will be summarized and analyzed using observed cases. Missing data will not be imputed.

The number and percentage of subjects with answers in each level of the EQ-5D-5L dimensions (Mobility, Self-care, Usual activities, Pain/Discomfort, and Anxiety/Depression) will be summarized with descriptive statistics during the Treatment Period. No comparisons or statistical tests will be performed.

Subject's responses to the EQ-5D-5L will be combined into a unique health state, which consists of a 5-digit code with 1 digit from each of the 5 dimensions at each scheduled assessment during the Treatment Period. The EQ-5D-5L states will be converted into a single preference-weighted health utility index score by application of country-specific weights (if available) or US weights if country-specific weights are unavailable.

During the 12-month placebo-controlled Treatment Period, the change from baseline to each scheduled assessment for health utility index score and EQ VAS will be analyzed using ANCOVA with treatment as the main effect and baseline as a covariate. The LS mean and standard error will be reported for each treatment group; the LS mean of treatment difference and associated 95% CI and P value will be reported comparing elagolix plus E2/NETA group with placebo.

In addition, the change from baseline to each scheduled assessment for health utility index score and EQ VAS will be summarized with descriptive statistics during the Treatment Period. No comparisons or statistical tests will be performed.

8.5.6 Work Productivity and Activity Impairment Questionnaire: Specific Health Problem (WPAI:SHP)

Each of the 4 measures of the WPAI:SHP data (work time missed, impairment while working, overall work impairment, and activity impairment) will be summarized and analyzed using observed cases. Missing data will not be imputed.

During the 12-month placebo-controlled Treatment Period, the change from baseline to each scheduled assessment for each of the measures as presented in the scoring guide will be analyzed using ANCOVA with treatment as the main effect and baseline as a covariate. The LS mean and standard error will be reported for each treatment group; the LS mean of treatment difference and associated 95% CI and P value will be reported comparing elagolix plus E2/NETA group with placebo.

In addition, the change from baseline to each scheduled assessment for each of the measures as presented in the scoring guide will be summarized with descriptive statistics during the Treatment Period. No comparisons or statistical tests will be performed.

8.5.7 PROMIS Fatigue Short Form 6a

The PROMIS Fatigue Short Form 6a will be summarized and analyzed using observed cases. Missing data will not be imputed.

During the 12-month placebo-controlled Treatment Period, the change from baseline to each scheduled assessment for PROMIS Fatigue Short Form 6a T-score will be analyzed using ANCOVA with treatment as the main effect and baseline as a covariate. The LS mean and standard error will be reported for each treatment group; the LS mean of treatment difference and associated 95% CI and P value will be reported comparing elagolix plus E2/NETA group with placebo.

In addition, the change from baseline to each scheduled assessment for PROMIS Fatigue Short Form 6a T-score will be summarized with descriptive statistics during the Treatment Period. No comparisons or statistical tests will be performed.

8.5.8 Health Care Resource Utilization Questionnaire (HCRU)

HCRU data will be summarized using observed cases. Missing data will not be imputed.

HCRU data will be summarized with descriptive statistics by Visit during the Treatment Period. The total number and percentage of Non-Study Health Care Practitioner visits and endometriosis-related Non-Study Health Care Practitioner visits overall and by the type of facility will be summarized. In addition, the number and percentage of subjects with Non-Study Health Care Practitioner visits and endometriosis-related Non-Study Health Care Practitioner visits overall and by the type of facility will be summarized.

The number and percentage of subjects seen at office will be presented by the type of Non-Study Health Care Practitioner and endometriosis-related Non-Study Health Care Practitioner who administered care to the subject. In addition, number of Non-Study Health Care Practitioner visits and endometriosis-related Non-Study Health Care Practitioner visits by practitioner will be summarized.

The number and percentage of subjects will be presented by the type of diagnostic or therapeutic procedures and endometriosis-related diagnostic or therapeutic procedures by visit during the Treatment Period. No statistical tests will be performed.

8.5.9 Hospitalization

Hospitalization related data will be summarized using observed cases. Missing data will not be imputed. Hospitalization data will be summarized with descriptive statistics during the Treatment Period based on the Adverse Events eCRF. No statistical tests will be performed.

The number and percentage of subjects who were hospitalized or had prolonged hospitalization will be summarized by treatment group. If a subject was hospitalized or

had prolonged hospitalization multiple times during the Treatment Period, she will be counted only once.

The number of hospitalizations will be summarized by treatment group. In addition, the number of days in hospital (i.e., discharge date – admission date + 1) will be summarized by treatment group. Only hospitalizations with admission date on or after the first dose date and within 30 days following the last dose date (i.e., first dose date \leq admission date \leq last dose date + 30) will be included in the analysis of the number of days in hospital. If discharge date or admission date is missing, then the hospitalization will be excluded from the analysis of the number of days in hospital.

8.6 Efficacy Subgroup Analyses

For each co-primary endpoint, the following subgroups will be explored to assess potential differences in treatment effect across subgroup levels. The subgroup analyses will be performed at Month 6, which represents the study visit for statistical evaluation of the co-primary efficacy endpoints.

- Baseline BMI: < median, \geq median
- Baseline BMI category: Normal (< 25 kg/m²), Overweight (25 – < 30 kg/m²), Obese (\geq 30 kg/m²)
- Race: Black or African American, Not Black or African American
- Baseline Age: < 25 years old, 25 – \leq 35 years old, > 35 years old.

The subgroup analysis will consist of a logistic regression with overall responder as the response variable, baseline value as a covariate, subgroup and treatment as main effects, and a treatment by subgroup interaction term.

9.0 Safety Analyses

9.1 General Considerations

Safety summaries will be provided separately using the Safety Analysis Set during the placebo-controlled Treatment Period, Safety Analysis Set during the open-label Treatment

Period, and All Elagolix plus E2/NETA Analysis Set as defined in Section 4.0. Unless otherwise specified, no statistical comparisons or tests will be performed on Safety Analysis Set during the open-label Treatment Period or the All Elagolix plus E2/NETA Analysis Set.

Unless otherwise specified, the baseline for the 12-month placebo-controlled Treatment Period will be the last non-missing value obtained prior to or on Study Day 1. The baseline during the open-label Treatment Period will be the last non-missing value obtained prior to or on the initiation day of elagolix (either elagolix alone or elagolix plus E2/NETA). The baseline for All Elagolix plus E2/NETA Analysis Set will be the last non-missing value obtained prior to or on the initiation day of elagolix plus E2/NETA.

All safety analyses will be based on observed data. Unless otherwise specified, missing data will not be imputed.

9.2 Adverse Events

Adverse events (AEs) will be summarized and presented using primary MedDRA System Organ Classes (SOCs) and preferred terms (PTs) according to the version of the MedDRA coding dictionary used for the study at the time of database lock. The actual version of the MedDRA coding dictionary used will be noted in the AE tables and in the clinical study report. Specific adverse events will be counted once for each subject for calculating percentages, unless stated otherwise. In addition, if the same adverse event occurs multiple times within a subject, the highest severity and level of relationship to investigational product will be reported.

9.2.1 Treatment-Emergent Adverse Events

Treatment-emergent adverse events (TEAEs) for each safety population are defined as follows:

TEAEs during the 12-month placebo-controlled Treatment Period on Safety Analysis Set during the placebo-controlled Treatment Period

TEAEs during the 12-month placebo-controlled Treatment Period are defined as any AEs with the onset that is on or after the first dose of study drug during the 12-month placebo-controlled Treatment Period and no more than 30 days after the last dose of study drug for subjects who premature discontinue during the 12-month double-blind Treatment Period or until the first dose of study drug in the open-label Treatment Period for subjects who enter the open-label Treatment Period. AEs starting more than 30 days following discontinuation of study drug will not be included in summaries of treatment-emergent AEs but will be summarized separately.

TEAEs during the open-label Treatment Period on the Safety Analysis Set during the open-label Treatment Period

TEAEs during the open-label Treatment Period are defined as any AEs with the onset that is on or after the first dose of study drug during the open-label Treatment Period and no more than 30 days after the last dose of study drug in the study. AEs starting more than 30 days following discontinuation of study drug will not be included in summaries of treatment-emergent AEs but will be summarized separately.

TEAEs for All Elagolix plus E2/NETA Analysis Set

TEAEs for All Elagolix plus E2/NETA Analysis Set are defined as any AEs with the onset that is on or after the first dose of elagolix plus E2/NETA (either in the placebo-controlled Treatment Period or open-label Treatment Period) and no more than 30 days after last dose of elagolix plus E2/NETA. AEs starting more than 30 days following discontinuation of study drug will not be included in summaries of treatment-emergent AEs but will be summarized separately.

The number and percentage of subjects experiencing treatment-emergent AEs will be summarized overall, as well as by primary MedDRA SOC and PT by treatment group.

The SOC's will be presented in alphabetical order, and the PT's will be presented in alphabetical order within each SOC.

9.2.2 Adverse Event Overview

An overview of treatment-emergent AEs will be presented consisting of the number and percentage of subjects experiencing at least one event for each of the following AE categories:

- Any treatment-emergent AE
- Any treatment-emergent AE related to study drug according to the investigator
- Any severe treatment-emergent AE
- Any serious treatment-emergent AE
- Any treatment-emergent AE leading to discontinuation of study drug
- Any treatment-emergent AE leading to death
- Any treatment-emergent AE of special interest as specified in [Appendix B](#)
- All deaths

In addition, for subjects who received elagolix 200 mg BID alone at Study Day 1, an overview of AEs during the placebo-controlled Treatment Period will be summarized separately for the first 6-month and second 6-month.

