Study drug kits will be dispensed to subjects at each on-site visit with the exception of the final visit at Treatment Month 48. Subjects randomized to elagolix plus E2/NETA on Day 1 of the Treatment Period will continue with the same dosing regimen (dose and frequency) throughout the entire Treatment Period; subjects randomized to elagolix 200 mg BID alone during the first 6 months will be reassigned to receive elagolix 200 mg BID plus E2/NETA (1 mg/0.5 mg) QD for the remainder of the Treatment Period (Months 7 – 48); subjects randomized to placebo will be reassigned at Treatment Month 12 to receive elagolix 200 mg BID plus E2/NETA (1 mg/0.5 mg) QD for the remainder of the Treatment Period. All subjects will know they are receiving elagolix 200 mg BID plus E2/NETA (1 mg/0.5 mg) QD during Months 13 – 48.

Through Treatment Month 12, subjects will use the daily e-Diary to continue recording:

- endometriosis-associated pain (DYS and NMPP via the 4 point Endometriosis Daily Pain Impact Scale) (no pain, mild pain, moderate pain, severe pain coded as 0 – 3)
- dyspareunia via a 4-point scale (no pain, mild pain, moderate pain, severe pain coded as 0-3, and not applicable)
- the presence of uterine bleeding (menstrual period and other uterine bleeding) and intensity of bleeding (spotting, light, medium, heavy)
- use of protocol specific analgesic rescue medications for endometriosisassociated pain

[figure not shown]
At the Day 1 visit (prior to dosing) and at all monthly visits during the Treatment Period (on-site and phone contacts), site staff will administer to subjects the overall endometriosis-associated pain questionnaire, an 11-point numeric rating scale (NRS).

Information regarding the use of rescue analgesic medications for endometriosisassociated pain will be collected at monthly study visits and recorded in source documents and eCRF.

At select study visits, subjects will be asked to complete various patient-reported outcome (PRO) questionnaires, including a Patient Global Impression of Change (PGIC). Vital signs assessments will be conducted at designated time points. Additional safety assessments including mammograms, TVUs, Pap tests, endometrial biopsies, and DXAs are completed as appropriate throughout the Treatment Period.

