2.0 Study Design, Objectives and Procedures

2.1 Objectives

The objectives of this study are to:

- Assess the safety and efficacy of elagolix 200 mg administered twice daily (BID) in combination with estradiol 1 mg/0.5 mg norethindrone acetate (E2/NETA 1 mg/0.5 mg) QD compared to placebo at 6 months and 12 months;
- Assess the effect of elagolix 200 mg BID in combination with E2/NETA (1 mg/0.5 mg) QD on bone mineral density (BMD) compared to elagolix 200 mg BID alone at 6 months and compared to placebo at 6 months and 12 months;

- Evaluate the continued safety and efficacy of elagolix 200 mg BID plus E2/NETA (1 mg/0.5 mg) QD for up to 48 months in premenopausal women with moderate to severe endometriosis-associated pain.

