6.0 Study Drug Duration

Duration (days) of treatment will be summarized for the Safety Analysis Set using the number of subjects treated, mean, standard deviation, median, minimum and maximum.

Study drug duration will be summarized as follows:

Placebo-controlled Treatment Period (Safety Analysis Set):

Duration of treatment during the placebo-controlled Treatment Period is defined as follow:

- For subjects who did not continue into the open-label Treatment Period:
 - Last dose date during the placebo-controlled Treatment Period – First dose date during the placebo-controlled Treatment Period + 1
- For subjects who continued into the open-label Treatment Period:
Minimum of
 - Last dose date during the placebo-controlled Treatment Period – First dose date during the placebo-controlled Treatment Period + 1

- First dose date during the open-label Treatment Period – First dose date during the placebo-controlled Treatment Period.

In addition, the number and percentage of subjects in each treatment duration interval (1 – 28 days, > 28 – 56 days, > 56 – 84 days, > 84 – 112 days, > 112 – 140 days, > 140 – 168 days, > 168 days) will be summarized.

Open-label Treatment Period (Safety Analysis Set):

Duration of treatment during the open-label Treatment Period is defined as last dose date during the open-label Treatment Period minus first dose date during the open-label Treatment Period plus 1 day.

In addition, the number and percentage of subjects in each treatment duration interval (1 – 84 days, > 84 – 168 days, > 168 – 252 days, > 252 – 336 days, > 336 – 420 days, > 420 – 504 days, > 504 – 588 days, > 588 – 672 days, > 672 – 756 days, > 756 – 840 days, > 840 – 924 days, > 924 – 1008 days, > 1008 days) will be summarized.

All Elagolix plus E2/NETA Analysis Set:

For subjects who received at least 1 dose of elagolix plus E2/NETA (either in the placebo-controlled or open-label Treatment Periods), the duration of treatment is defined as the last dose date of receiving elagolix plus E2/NETA minus the first dose date of receiving elagolix plus E2/NETA plus 1 day.

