9.2.3 Treatment-Emergent Adverse Events by SOC and PT

Treatment-emergent adverse events will be summarized by SOC and PT; by maximum relationship to study drug as assessed by the investigator (e.g., reasonable possibility or no reasonable possibility) and SOC and PT; by maximum severity and SOC and PT; and by subject number and SOC and PT. Specific adverse events will be counted once for each subject for calculating percentages, unless stated otherwise. In addition, if the same adverse event occurs multiple times within a subject, the highest severity and level of relationship to investigational product will be reported.

In addition, treatment-emergent adverse events will be summarized by PT and sorted by decreasing frequency for the elagolix plus E2/NETA group.

In addition, for subjects who received elagolix 200 mg BID alone at Study Day 1, TEAEs during the placebo-controlled Treatment Period will be summarized separately for the first 6-month and second 6-month by SOC and PT.

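### Adverse-event tables are split at Month 6 only for the elagolix-alone arm, so its pre-switch incidence has no same-length comparator and its 12-month column mixes two regimens

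*SAP*

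**What the plan says.** Protocol 5.1 states that "subjects randomized to elagolix 200 mg BID alone during the first 6 months will be reassigned to receive elagolix 200 mg BID plus E2/NETA" for Months 7 to 48. SAP 4.0 labels safety groups by the treatment received at randomisation, so these women stay in the elagolix-alone column after the switch.

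SAP 9.2.1 defines treatment-emergent events over the whole placebo-controlled period, and subjects with events "will be summarized overall, as well as by primary MedDRA SOC and PT by treatment group". SAP 9.2.2 then adds, only for women who started on elagolix alone, that "an overview of AEs during the placebo-controlled Treatment Period will be summarized separately for the first 6-month and second 6-month". SAP 9.2.3 adds that, for the same women, "TEAEs during the placebo-controlled Treatment Period will be summarized separately for the first 6-month and second 6-month by SOC and PT". Neither sentence extends to the other two arms. SAP 9.2.5 (serious events, discontinuations, deaths) and 9.2.6 (AESIs by SOC and PT) mention no Month 6 cut for any arm.

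The first objective in SAP 2.1 is safety and efficacy of the combination "compared to placebo at 6 months and 12 months". In SAP 6.0 the last two exposure classes for the placebo-controlled period read "> 140 – 168 days, > 168 days) will be summarized".

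**The concern.** Day 1 to Month 6 is the only window in which elagolix with and without add-back run concurrently under randomisation. The SAP recognises that the switch makes the 12-month elagolix-alone column hard to interpret, and isolates the first half for that arm. A first-half column needs a first-half column beside it, and the SAP does not plan one for the combination or for placebo.

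Someone wanting to know whether add-back changes AE incidence has two options: set six months of elagolix alone against twelve months of another arm, or use a 12-month column that is half elagolix alone and half combination. The first differs in length of observation, the second in regimen. The missing table is also the one that would show AE incidence for the combination against placebo at 6 months, which the first objective names.

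**Working it through.** **Step 1. What each AE output covers.**

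| Output | Elagolix alone | Combination | Placebo |
|---|---|---|---|
| Overview (9.2.2) | 12 months and each half | 12 months | 12 months |
| SOC/PT (9.2.3) | 12 months and each half | 12 months | 12 months |
| Serious events, discontinuations (9.2.5) | 12 months | 12 months | 12 months |
| AESIs by SOC and PT (9.2.6) | 12 months | 12 months | 12 months |
| Events per 100 patient-years (9.2.4) | only from first combination dose | all combination exposure | only from first combination dose |
| Hot flash and night sweat counts (9.2.7) | each time point | each time point | each time point |

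No row gives AE incidence over the first six months in more than one arm. The exposure-adjusted rates do not help: they exclude the elagolix-alone phase and placebo exposure, and they pool combination exposure across the study.

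**Step 2. Inputs.** The documents give no AE rates, so the plan has no figure on this point to reproduce. Its one computed design figure, power above 90% for the co-primary endpoints, does reproduce (0.994 for NMPP, above 0.9999 for DYS, with 400 and 200 women) but has no bearing here. All rates below are assumed.

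**Step 3. A true doubling under constant hazards.** Take 12-month incidence on the combination as 20%, and twice that hazard on elagolix alone until the switch.

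- Six-month cumulative hazard, combination: −ln(0.80)/2 = 0.1116, so 6-month incidence = 1 − exp(−0.1116) = 10.6%.
- Elagolix alone, first six months: 1 − exp(−2 × 0.1116) = 20.0%.
- Elagolix-alone column over 12 months, with the combination hazard after the switch: 1 − exp(−(0.2231 + 0.1116)) = 28.4%.

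| Reading | Elagolix alone | Combination | Ratio |
|---|---|---|---|
| 6 months v 6 months | 20.0% | 10.6% | 1.9 |
| 6 months v 12 months | 20.0% | 20.0% | 1.0 |
| 12-month mixed v 12 months | 28.4% | 20.0% | 1.4 |

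**Step 4. No true difference.** With the same constant hazard in every arm, p6 = 1 − √(1 − p12). For 12-month incidence of 10%, 20%, 30% and 50%, the 6-month incidence is 5.1%, 10.6%, 16.3% and 29.3%. A 6-versus-12-month reading then shows elagolix alone lower by 4.9, 9.4, 13.7 and 20.7 percentage points from window length alone.

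**Step 5. What the mixed column estimates.** Let six-month risk on elagolix alone be 30% and new-onset risk in the following six months on the combination be 5% to 15%. The column reads 1 − 0.70 × 0.95 = 33.5% to 1 − 0.70 × 0.85 = 40.5%. Twelve months of elagolix alone would give 1 − 0.70² = 51%; twelve months of the combination would give 1 − 0.95² = 9.8% to 1 − 0.85² = 27.8%. The column estimates neither regimen.

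**Step 6. Front-loading.** If 90% of a 20% 12-month incidence starts in the first half, 6-month incidence is 0.9 × 20% = 18%, and the window gap falls from 9.4 to 2 points. If every event starts in the first half, neither reading is distorted.

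**Step 7. Exposure classes.** Protocol 1.3 defines a month as 28 days, so 6 months is 168 days and 12 months is 336. The top class in SAP 6.0 puts everyone treated for more than 168 days together.

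**The case against.** The case for leaving the tables alone is substantial.

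- The split can be read as a within-arm description. No SAP text sets six months of elagolix alone against twelve months of another arm. Protocol 8.1.1 makes combination versus placebo the primary safety comparison and rules out tests between the two elagolix groups unless otherwise specified; SAP 10.0 calls elagolix alone a reference arm. The only objective that compares the two elagolix regimens is BMD at Month 6, and SAP 9.5.2.1 provides that comparison. All of this stands. A reader might infer that the plan itself makes a mismatched comparison; it does not. It leaves no matched one available.
- Hot flashes and night sweats are partly covered: SAP 9.2.7 gives counts by severity, group and time point, plus time to first onset of the corresponding AEs. It would be wrong to say that nothing on vasomotor effects can be compared before the switch. The gap concerns AE incidence tables.
- The overview split for the elagolix-alone arm includes a line for any AESI, and its split SOC/PT table shows individual terms. A claim that AESIs are unsplit for every arm would be too strong; it is the dedicated 9.2.6 tables that have no cut.
- The 6-month safety objective is not wholly unserved. SAP 9.5.2.1 compares BMD with placebo at Month 6, and SAP 9.3 and 9.4 give differences from placebo by visit for selected laboratory variables and vital signs.
- The mixed column follows the protocol, which summarises by Day 1 assignment and describes this arm as elagolix alone for the first six months. That makes the column legitimate. It does not make it an estimate of elagolix alone.

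**Conclusion.** The point holds for AE incidence. The elagolix-alone phase has no concurrent comparator of equal length, the 12-month elagolix-alone column mixes two regimens, and no AE incidence table addresses 6-month safety against placebo.

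The size cannot be known from the documents. Under constant hazards and a true doubling, a ratio of 1.9 would read as 1.0 or 1.4; under equal hazards, a false gap of 4.9 to 13.7 points would appear for 12-month incidences of 10% to 30%. Strong front-loading makes both small. It may be tempting to conclude that a benefit of add-back will be hidden. The documents do not support that as a fact: a 6-versus-12-month reading can only lower elagolix alone relative to its comparator, but by how much depends on event timing, and the mixed column depends also on what happens after the switch.

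The primary 12-month comparison of combination with placebo uses equal windows and is unaffected, as are the co-primary, key secondary and BMD analyses. The change should be made, but the validity of the trial does not turn on it. The coarse exposure class is a minor companion matter, since SAP 6.0 also gives mean, SD, median and range.

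**What to change.** In SAP 9.2.2, 9.2.3 and 9.2.6, produce the AE overview, SOC/PT and AESI tables for all three arms in two windows: first dose to the Month 6 switch (or Day 168), and from then to the end of the placebo-controlled period. Use as each window's denominator the women dosed in it. State which window takes an event that starts close to the switch or within 30 days of an early stop. The overview already has lines for serious events and discontinuations, so those are covered at summary level.

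Label the third arm as elagolix alone, then combination, in the 12-month and Months 7–12 tables. Use the first-window table for the AE part of the 6-month safety objective and for describing combination against elagolix alone.

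As a minor addition, extend the placebo-controlled duration classes in SAP 6.0 from 168 to 336 days in 28-day steps.

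The cost is SAP wording and a few more tables from data already collected. They are descriptive, so they use no alpha. If the 12-month analysis has already been run, add them as labelled supplementary tables.
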